### 5.3.2 Dose Reductions

Standard dose reductions for Azacitidine will occur as follows:

If blood counts at time of baseline PD draw WBC  $\geq 3.0 \times 10^9/L$ , ANC  $\geq 1.5 \times 10^9/L$ , and platelets  $\geq 75.0 \times 10^9/L$  adjust the dose as follows, based on nadir counts for any given cycle:

Nadir Counts		% Dose in the Next Course
ANC (<math>\times 10^9/L</math>)	Platelets (<math>\times 10^9/L</math>)	
<0.5	<25.0	50%
0.5 – 1.5	25.0-50.0	67%
>1.5	>50.0	100%

For patients whose baseline counts are WBC  $<3.0 \times 10^9/L$ , ANC  $<1.5 \times 10^9/L$ , or platelets  $<75.0 \times 10^9/L$ , dose reductions will be at the discretion of the treating physician.

At the discretion of the treating physician cycles may be spaced out to up to 42 days apart based upon hematologic response and recovery between cycles.

Renal Toxicity - If unexplained reductions in serum bicarbonate levels to  $<20$  mEq/L occur, the dosage should be reduced by 50% on the next course. If increases in BUN or serum creatinine (unexplained) occur, delay next cycle until values reach baseline or normal, then reduce dose by 50% for next treatment course.

### 5.3.3 Antibiotic Prophylaxis

- All patients should be treated with acyclovir 400mg BID unless tested and found to be HSV antibody negative.
- The recommended antibiotic prophylaxis is as follows, (but may be determined by physician discretion): ciprofloxacin and augmentin for severely neutropenic patients; fluconazole 400mg daily; and acyclovir 400mg twice daily.
- Voriconazole, fluconazole or posaconazole may NOT be used within 72 hours (prior to or after receiving) Rapamycin. If suspected or proven Aspergillosis infection occurs- Anidulofungin, Caspofungin or Amphotericin B may be used, as per the physician's discretion.

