### 4.2 Exclusion Criteria

1. Patients must not be currently receiving any chemotherapy agents (except Hydroxyurea)
  - a. Intrathecal ARA-C and intrathecal methotrexate are permissible (as they are not systemic and only isolated to the central nervous system).

- b. Patients cannot have received more than 3 prior lines of therapy for their hematologic malignancy. Patient may have previously had azacitidine or decitabine will be eligible to enroll on Arm A (MDS).
2. Patients must not be receiving growth factors.
3. Patients with a current second malignancy requiring systemic therapy, other than non-melanoma skin cancers, are not eligible. If a patient has had a prior second malignancy that is not currently requiring active treatment, the patient will be considered eligible.
4. Patients with uncontrolled high blood pressure, unstable angina, symptomatic congestive heart failure, myocardial infarction within the past 6 months or serious uncontrolled cardiac arrhythmia are not eligible.
5. Patients may not take any of the following medications while on study, but will be considered eligible if medication is discontinued 72 hours prior to first dose of Sirolimus:
  - Carbamazepine (e.g. Tegretol)
  - Rifabutin (e.g. Mycobutin)
  - Rifampin (e.g. Rifadin)
  - Rifapentine (e.g. Priftin)
  - St. John's Wort- may decrease effects of sirolimus by decreasing the amount of sirolimus in the body
  - Clarithromycin (e.g. Biaxin)
  - Cyclosporin e.g. (Neorla or Sandimmune)
  - Diltiazem (e.g. Cardizem)
  - Erythromycin (e.g. Akne-Mycin, Ery-Tab)
  - Itraconazole (e.g. Sporonox)
  - Fluconazole (e.g. Diflucan)
  - Ketoconazole (e.g. Nizoral)
  - Telithromycin (e.g. Ketek)
  - Verapamil (e.g. Calan SR, Isoptin, Verelan)
  - Voriconazole (e.g. VFEND) - May increase the effects of sirolimus by increasing the amount of this medicine in the body. Can take 72 hours after last dose of Sirolimus
  - Tacrolimus (e.g. Prograf) – May cause liver transplant rejection or serious side effects in patients on sirolimus.
6. Patients with known HIV positivity or AIDS-related illness are not eligible.
7. Patients with other severe concurrent disease which in the judgment of the investigator would make the patient inappropriate for entry into this study are ineligible.
8. Patients must not have received any investigational agents within 21 days of study entry.

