### **5 Study Drug**

#### **5.1 Sirolimus**

Drug Name: Sirolimus

Other Names: Rapamycin, Rapamune®

Classification: Immunosuppressant Agent

Mode of Action: Rapamycin inhibits T-lymphocyte activation and proliferation in response to antigenic and cytokine stimulation. Its mechanism differs from other immunosuppressants.

Storage and Stability: Store at room temperature, 20°C to 25°C (68°F to 77°F); protect from light.

Dose Specifics: Assigned dose level. Patients will receive a 12mg loading dose of sirolimus. They will then receive a 4mg daily dose of sirolimus beginning 24 hours after the loading dose for the number of days indicated by protocol regimen.

Preparation 1 and 2 mg tablet

Route of Administration: All drug is to be taken by mouth. Doses should be given every 24 hours  $\pm$  2 hours. The drug should be consistently without food. Rapamycin will be given every 24 hours for number of days indicated by protocol regimen.

Incompatibilities: Diltiazem increases serum concentrations of sirolimus. Sirolimus serum concentrations may be increased with use of voriconazole, itraconazole, ketoconazole and fluconazole. Concurrent use of these drugs is contraindicated.

Availability: Available as Rapamune® 1mg tablet and 2mg tablets. Will be available through the Investigational Drug Services.

Side Effects

**Common** (21-100% Frequency) Immediate: Nausea, Vomiting Prompt: Within 2-3 weeks, prior to next course. Diarrhea, Hypertension, Increased creatinine Delayed: Any time after above.

Hypercholesterolemia, Hypertriglyceridemia

**Occasional** (5-20% Frequency) Immediate: Rash Prompt: Within 2-3 weeks, prior to next course.

Infections; edema; weight gain, arthralgia; tremor; acne; myelosuppression; fever; abdominal pain; myalgia; hypokalemia; hypophosphatemia Delayed: Any time after above. Stomatitis

**Rare** (< 5% Frequency) Hepatotoxicity Delayed: Any time after above. Hirsutism, Secondary Lymphoma, Inflammation of the lungs

Nursing/Patient Implications: Monitor blood pressure, and serum creatinine.

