## **5.6 Prior and Concomitant Therapy**

1. Information of prior cytotoxic regimens will be collected.
2. All concomitant medical therapy will be collected as part of the history.
3. All concomitant medicines/therapies are permitted during the study except for those noted in the exclusion criteria in section 4.2.
4. No concomitant voriconizole, posaconazole, itraconazole, ketokonazole, or diltiazem within 72 hours prior to or after receiving a dose of rapamycin.
5. All patients should receive acyclovir unless documented to be HSV negative.

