### **Attachment # 3: Admissions Plan**

#### **Non Emergent and Emergent**

#### **Procedure for transitioning patients from outpatient to inpatient/ inpatient to outpatient on [name] trials:**

- 1.) If participant begins the trial as an outpatient the investigator will handwrite prescription for Sirolimus.
- 2.) If planned admission occurs, the outpatient investigator will notify the inpatient team (Preferably the attending or NP team) of the pending admission along with the following information:
  - a. The date that the intended transfer will take place
  - b. The day of treatment the patient is on
- 3.) The inpatient attending will be responsible for placing all orders\* related to the patient's treatment while being treated in-patient on study, including but not limited to, sirolimus dosing, chemo administration and PK/PD orders. This may be delegated to a fellow/nurse practitioner under the direct management of the attending physician.
- 4.) Upon discharge, treating physician or designee must notify study coordinator. Hospital discharge planning must include outpatient follow up appointments for study required visit dates. Please note: weekend discharges may result in multiple protocol violations. Additionally, protocol prohibits use of azoles or diltiazem until 72 hours following LAST dose of sirolimus.

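### Fluconazole is recommended daily with no exception for sirolimus days, while the next bullet and other sections restrict it around sirolimus and the lists of restricted azoles differ

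*Combined protocol and SAP*

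**What the plan says.** Section 5.3.3 introduces its prophylaxis regimen with "The recommended antibiotic prophylaxis is as follows, (but may be determined by physician discretion". The regimen includes "fluconazole 400mg daily; and acyclovir 400mg twice daily". That bullet says nothing about which days of the cycle it applies to. The next bullet reads "Voriconazole, fluconazole or posaconazole may NOT be used within 72 hours (prior to or after receiving) Rapamycin".

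Four other places bear on the same drug or class:

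- Section 4.2, item 5, opens with "Patients may not take any of the following medications while on study" and its list includes "Fluconazole (e.g. Diflucan". The item accepts patients who stop a listed drug 72 hours before the first sirolimus dose. A note allowing restart 72 hours after the last dose is printed only in the voriconazole entry.
- Section 5.1 says voriconazole, itraconazole, ketoconazole and fluconazole may increase sirolimus concentrations, and adds "Concurrent use of these drugs is contraindicated".
- Section 5.6, item 4, states "No concomitant voriconizole, posaconazole, itraconazole, ketokonazole, or diltiazem within 72 hours prior to or after receiving a dose of rapamycin". Fluconazole is not named there, but item 3 of the same section bars whatever section 4.2 lists.
- Attachment 3 states that the "protocol prohibits use of azoles or diltiazem until 72 hours following LAST dose of sirolimus". Its order prompt and nursing note repeat the class-wide restriction, and the prompt starts it 72 hours before the first dose.

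**The concern.** A recommendation to give fluconazole every day, read beside a rule that bars it around every sirolimus dose, tells treating staff two incompatible things about one drug. The differing lists add a second uncertainty: which azoles are restricted depends on which section is consulted.

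The stakes come from the protocol's own statements. Section 5.1 says these drugs may raise sirolimus levels. Section 1.6 warns that sirolimus, as an immunosuppressant, may add to infectious toxicity. Section 3.2.2.2 plans no dose adjustment from the Day 4 sirolimus level, so a raised level would not lead to a planned correction. That same level is used in the PK/PD correlation (sections 3.2.2.2, 3.2.2.3 and 5.3.1). Azacitidine may be given at several network hospitals, and Attachment 3 leaves starting and stopping of azoles to treating physicians or nursing staff, who need a single rule to apply.

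**Working it through.** The plan states no figure to reproduce. The check sets the passages side by side and then counts days.

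**Which azoles are named**

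| Place | Fluconazole | Voriconazole | Itraconazole | Ketoconazole | Posaconazole | Window |
|---|---|---|---|---|---|---|
| 4.2 item 5 | yes | yes | yes | yes | no | on study; restart note in the voriconazole entry only |
| 5.1 | yes | yes | yes | yes | no | concurrent use |
| 5.3.3, restriction | yes | yes | no | no | yes | 72 h before or after sirolimus |
| 5.6 item 4 | no (item 3 brings in 4.2) | yes | yes | yes | yes | 72 h before or after a dose |
| Attachment 3 | class | class | class | class | class | 72 h before first dose to 72 h after last dose |

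No two of the three named combinations (4.2 and 5.1; 5.3.3; 5.6 item 4) are the same. Attachment 3 also does not say whether first and last dose refer to a cycle or to the whole of treatment.

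**How many days the 72-hour rule bars**

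Inputs: sirolimus on Days 1-10 with consecutive azacitidine or Days 1-12 with split azacitidine (sections 1.6 and 5.3.1); 28-day cycles that may be spaced up to 42 days (sections 1.6 and 5.3.2); a 72-hour (3-day) window on each side (section 5.3.3). Sirolimus is taken to be given at about the same time each day.

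Barred days per cycle = (last dose day − 1) + 3 + 3.

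- Days 1-10: 9 + 6 = 15 days. In a 28-day cycle the free span runs from Day 13 (10 + 3) to Day 26 (29 − 3), which is 13 days, and 28 − 13 = 15.
- Days 1-12: 11 + 6 = 17 days. The free span runs from Day 15 to Day 26, which is 11 days, and 28 − 11 = 17.

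| Sirolimus days | Barred | Share of 28-day cycle | Share of 42-day cycle |
|---|---|---|---|
| 1-10 | 15 | 15/28 = 54% | 15/42 = 36% |
| 1-12 | 17 | 17/28 = 61% | 17/42 = 40% |

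The barred days include every sirolimus day at either cycle length, so fluconazole given every day cannot satisfy the rule.

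**The case against.** The best defence is that the two bullets in section 5.3.3 belong together. On that reading the daily wording gives a dosing frequency, physician discretion makes the regimen optional, and the next bullet limits fluconazole to the days away from sirolimus. Sections 5.3.3 and 5.6 and Attachment 3 all work with 72 hours, and the order prompt and nursing note in Attachment 3 are real safeguards. No passage expressly permits an azole alongside sirolimus.

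Much of this stands and lowers the chance of error. It does not remove the contradiction. The recommendation carries no exception for sirolimus days, discretion does not define a permitted window, and section 4.2 read literally does not allow off-sirolimus use of fluconazole.

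A reader might also infer more than the text supports:

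- *That fluconazole is barred on every study day.* This takes section 4.2 at its most literal. The restart note in the voriconazole entry may have been meant for the inhibitors listed above it; the text is ambiguous.
- *That more than half of all days are always barred.* This holds for 28-day cycles. The share falls below half once a cycle exceeds 30 days (2 × 15) or 34 days (2 × 17).
- *That section 5.6 leaves fluconazole unrestricted.* Its item 3 brings in the section 4.2 list.
- *That the S6 result would be distorted.* Section 5.1 says only that levels may rise and gives no size. Section 1.5 reports, from five subjects, that adding rapamycin ex vivo gave no further S6 inhibition, and it regards in vivo inhibition at this dose as maximal. Day 4 sampling is in Cycle 1 only (section 6.1.1), so exposure in later cycles is irrelevant to it.

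**Conclusion.** The instructions contradict one another as written. The clearest case lies within section 5.3.3 itself, between adjacent bullets, and sections 4.2 and 5.1 and Attachment 3 extend it. The azole lists are also inconsistent, although section 5.6 item 3 largely closes the fluconazole gap in item 4. The conflict covers about 15 or 17 days of each cycle, assuming sirolimus at regular 24-hour intervals and the 72-hour rule applied to each cycle.

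The consequence is a patient-safety concern in kind. The documents do not quantify the rise in sirolimus, so no size can be given. An effect on the Cycle 1 Day 4 sirolimus level and its PK/PD correlation is possible but not shown, and nothing in the documents shows an effect on the primary response endpoint. Which clinical rule is right is not judged here.

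**What to change.** Reconcile sections 4.2, 5.1, 5.3.3, 5.6 and Attachment 3 into one list of restricted azoles with one stated window. The text should say whether the window applies per cycle or to the whole of treatment, and each section should refer to that list instead of repeating its own. The prophylaxis recommendation in section 5.3.3 needs to agree with it. The clinical team must decide the rule.

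For the analysis, add to section 7.2 a flag for Day 4 PK/PD samples from patients with azole exposure inside the window that the reconciled rule sets, so that the correlation can be shown with and without them.

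The protocol change is wording in five places. The cost of the flag is less certain. Section 5.6 collects concomitant therapy as part of the history and the schedule in Attachment 2 has no row for it, so the sponsor should confirm that azole use is recorded with dates. If it is not, start and stop dates around Cycle 1 Days 1-4 would have to be added to data collection.

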### 5.3.4 Supportive Care

- Growth factor support and transfusion of blood products will be performed as per physician discretion.
- Supportive care will be administered at the discretion of the patient's supervising attending.

### 5.3.5 Method for Assigning Subjects to Treatment Groups

This is an open label study of a single therapy regimen.

Once eligibility has been established and confirmed by signature of the Jefferson principal investigator, the Research Coordinator at TJU will then be assigned a registration number according to the subject's diagnosis (MDS or refractory AML). This number is unique to the participant on this trial and must be used moving forward (i.e. for CRF completion, SAE reporting, etc). As of October 2017 and July 2018, both Arm C and Arm B are closed to enrollment respectively. Patients with MDS who have received prior treatment will be allowed to enroll onto Arm A.

A master study enrollment log will be maintained by the study team at the Thomas Jefferson University.

Patients cannot be registered to this study on the weekends. The [name] lab at UPenn cannot accept samples after 1pm.

## **5.4 Preparation and Administration of Study Drug**

Sirolimus will be purchased from Wyeth and then stored and dispensed from the Investigational Drug Service (IDS). It will be dispensed in pill bottles containing a full cycle's amount of Sirolimus and the labeling will contain explicit dosing instructions. Subjects may start a cycle as an outpatient and will self-administer their Days 1 and 2 doses at home or in the clinic prior to azacitidine administration. At time of enrollment, the subject, the subject will receive a pill diary to record time of pill administration. The subject will be asked to bring their pill bottle as well as their pill diary to the infusion center or hospital depending on location of treatment with azacitidine.

## **5.5 Subject Compliance Monitoring**

Subjects will be asked to keep a pill diary to record the time of each dose of Sirolimus taken. If subject starts a cycle as an outpatient, they will self-administer their Days 1 and 2 doses. The subject will be asked to bring their pill bottle as well as their pill diary to the hospital at the time of admission. For the rest of the cycle, each daily dose will be administered by nurses in the inpatient setting.

Please see Attachment # 3 for emergent admission guidelines.

## **5.6 Prior and Concomitant Therapy**

1. Information of prior cytotoxic regimens will be collected.
2. All concomitant medical therapy will be collected as part of the history.
3. All concomitant medicines/therapies are permitted during the study except for those noted in the exclusion criteria in section 4.2.
4. No concomitant voriconizole, posaconazole, itraconazole, ketokonazole, or diltiazem within 72 hours prior to or after receiving a dose of rapamycin.
5. All patients should receive acyclovir unless documented to be HSV negative.

## **5.7 Packaging**

Available as Rapamune® 1mg tablet and 2mg tablets. Will be available through the Investigational Drug Services

## **5.8 Receiving, Storage, Dispensing and Return**

### **5.8.1 Receipt of Drug Supplies**

Upon receipt of the of the study treatment supplies, an inventory must be performed and a drug receipt log filled out and signed by the person accepting the shipment. It is important that the designated study staff counts and verifies that the shipment contains all the items noted in the shipment inventory. Any damaged or unusable study drug in a given shipment (active drug or comparator) will be documented in the study files. The investigator must notify study sponsor of any damaged or unusable study treatments that were supplied to the investigator's site.

### **5.8.2 Storage**

See section 5.1 for details.

## **6 Study Procedures**

At enrollment each subject will have a medical history taken, a physical exam (including neurological exam), vital signs, ECOG performance status, and laboratory studies including CBC with differential, liver function tests, electrolytes, uric acid, and glucose as well as a pregnancy test if applicable. An HSV titer is recommended. Patients who have not had a bone marrow biopsy sample within the last 4 weeks will require a bone marrow biopsy and aspirate.

Patients will be offered an option to complete the standard of care chemotherapy treatment at the following Jefferson Health network hospitals: Center City Hospital, Abington Hospital, Aria Hospital, Methodist Hospital and NJ Division (Kennedy) Hospital. All research related procedures are to be done at Jefferson Center City campus.

Patients will be followed for disease status and survival for 5 years following the enrollment of the last patient. These follow-ups will be via phone call, chart review, or in conjunction with their routine office visits every 3 months.

See Attachment #2 for Study Procedures Table.

## **6.1 Correlative Studies**

### **6.1.1 Biologic studies**

Within 4 weeks of beginning on study drugs, patients must have 5-10 ml of Bone Marrow Aspirate or 20ml of peripheral blood (if  $\geq 5000/\mu\text{l}$  peripheral blasts (WBC x blast percentage  $>0.5$  thousand/ $\mu\text{l}$ )), in a preservative-free heparin (green top) tube, sent to the Stem Cell Core at the University of Pennsylvania.

Peripheral blood samples will also be collected before the first sirolimus administration, and within 4 hours prior to Sirolimus dose on Day 4 of CYCLE 1 only (please see section 5.3.1 for details).

Both marrow and blood will be sent for any patient with a peripheral blast count  $\leq 5000/\mu\text{l}$  and  $\geq 200/\mu\text{l}$ .

Samples will then be analyzed by [name] lab. Samples are to be delivered to [name] laboratory ([name]).

Patient samples will be washed and lysed in 1% Triton X-100 lysis buffer. 100  $\mu\text{g}$  protein per lane will be analyzed using SDS-PAGE and Western blotting. Protein phosphorylation and expression will be examined using p70S6 kinase antibodies. Optical densitometry will be used to quantify the protein.

1-2 ml will be obtained from the whole blood or marrow samples drawn at baseline and day 4. These samples must contain at least  $\geq 200/\text{ml}$  (WBC x blast percentage  $>0.2$  thousand/ $\mu\text{l}$ ) Samples will be aliquotted as 100  $\mu\text{l}$  sample/tube into 5 ml tubes and a subset will be inhibited with 1  $\mu\text{M}$ rapamycin x 30 min or stimulated with the protein kinase C agonist phorbolmyristyl acetate (PMA) 40 nM x 10 min at 37°C to provide negative and positive S6 controls. Following this incubation, cells will be fixed with 4% formaldehyde for 10 minutes, followed by red blood cell lysis and permeabilization with 0.1% triton X-100 for 30 minutes at room temperature. Cells will be washed with cold PBS and 4% BSA and cell pellets frozen in an isotonic medium containing 20% serum and 10% glycerol. After baseline and day 4 samples are obtained, these samples will be thawed, washed with cold PBS and 4% BSA and proteins denatured by exposure to 50% methanol in 0.9% NaCL prior to antibody staining and data acquisition on a multi-color flow cytometer. Expression of cell surface epitopes CD45, 13, and 33 and intracellular phospho-S6 kinase will be acquired using CellQuest or DiVA software and data stored as ListMode files. FlowJo software will be used to analyze these data.

Gating upon cells with characteristics of myeloid blasts (CD45 dim positive, intermediate side scatter) and confirming surface expression of CD13 and/or 33 in comparison to internal negative controls for these epitopes (CD45 bright positive, low side scatter lymphocytes), identified leukemic blasts will be examined for phosphorylation of S6 kinase at baseline and day 4. A positive gate containing PMA stimulated blasts and a negative gate containing unstained ("fluorescence minus one") blasts will be used to score samples as to the percentage of blasts that are positive or negative for S6 phosphorylation. Baseline and day 4 samples will be compared for the relative percentages of cells within these gates as an indication of in vivo S6 inhibition in leukemic blasts by rapamycin. Median fluorescence intensity will also be acquired for S6 phosphorylation and compared for the baseline and day 4 samples.

